4.8.1.1 Subsets for AE Descriptive Presentation

- Separate summary tables by SOC and PT will be presented for treatment-emergent SAEs.
- Separate summary tables by SOC and PT and by SOC, PT and maximum severity will be presented for related TEAEs.
- Separate summary tables by SOC and PT will be presented for treatment-emergent related SAEs.
- Separate summary tables by SOC and PT will be presented for treatment-emergent AEs leading to the permanent discontinuation of IMP. An AE leading to discontinuation is an AE with action taken with IMP equal to “Permanently discontinued”.

CONFIDENTIAL

Sponsor:	Zambon S.p.A.	Protocol Number:	Z7224L02
----------	---------------	------------------	----------

- Separate summary tables by SOC and PT will be presented for treatment-emergent fatal SAEs.
- Treatment-emergent SAEs and fatal AEs will be listed separately.
- The most frequent MedDRA PTs ($\geq 5\%$ of subjects with events in any treatment group) will be presented overall and by treatment. PTs will be used for tabulation, sorted by decreasing overall frequency.

All other information collected will be listed, as appropriate. Additionally, listings will display relative day of AE onset.

The relative day of AE onset will be calculated as follows:

- For pre-treatment AEs:
 - AE onset date - date of first IMP dose (if AE onset date is completely known);
 - missing (if AE onset date is incomplete or unknown).
- For TEAEs:
 - AE onset date - date of first IMP dose +1 (if AE onset date is completely known);
 - missing (if AE onset date is incomplete or unknown).

Notes:

- AEs will be coded using MedDRA version 19.1 or higher (please refer to the final Data Management Plan for the latest coding information).
- Terms will be displayed in descending overall frequency (and then alphabetically) of SOCs and in descending overall frequency (and then alphabetically) of PTs within each SOC.

4.8.2 Spirometry Results

The following spirometry parameters will be summarised for each visit, as applicable, by treatment group and overall:

- FEV₁ (L);
- Predicted FEV₁ (%);
- FVC (L);
- Predicted FVC (%);
- Change in FEV₁ (L) from pre-salbutamol/albuterol intake to 30 minutes post-IMP.

Absolute value and change from baseline at each visit will be described by means of summary statistics for continuous variables.

The number and percentages (along with exact 95% CIs) of subjects experiencing bronchospasm at Visit 7 (End of Treatment) following IMP administration as clinically (as collected in the Spirometry eCRF forms) or spirometrically ($>15\%$ decrease in FEV₁ from pre-

CONFIDENTIAL

Sponsor:	Zambon S.p.A.	Protocol Number:	Z7224L02
----------	---------------	------------------	----------

salbutamol/albuterol intake to 30 minutes post-IMP) determined will be summarised by treatment. The number of subjects experiencing bronchospasm at all other visits will be listed. The subject will be considered spirometrically to have had a bronchospasm if presenting >15% decrease in FEV₁ from pre-salbutamol/albuterol intake to 30 minutes post-IMP or a positive answer to the above question.

The relative risk for colistimethate sodium/placebo will be provided with 95% asymptotic CIs. Treatment differences will be assessed using a Fisher Exact test. Subjects with no available result will be excluded from the analysis.

Notes:

- Change in FEV₁ (L) will be calculated as FEV₁ 30 minutes post-IMP – FEV₁ pre-salbutamol/albuterol intake;
- Percentage change in FEV₁ (%) will be calculated as 100*(change in FEV₁ [L] / FEV₁ pre-salbutamol/albuterol intake).

4.8.3 [CCI] [CCI] to Colistimethate Sodium

The number and percentage of subjects whose [CCI] [CCI] as per data received from Eurofins central laboratory) [CCI] at the end of treatment (at 12 months [Visit 7]) will be presented overall and by treatment. Results will be presented along with number and percentage of subjects with result to susceptibility testing equal to “[CCI]”, “Moderate” and “NA”.

The summary will be repeated by status of previous usage of colistimethate sodium/colistin as detailed in Section 4.1.5.

Missing data will not be imputed. A separate summary will be presented summarising the last available results for each subject.

Notes:

- Based on data collected on the Non-CF Bronchiectasis History eCRF form regarding previous usage of colistimethate sodium/colistin, subjects will be classified into:
 - Without any previous usage of colistimethate sodium/colistin;
 - With previous usage of colistimethate sodium/colistin;
 - With missing data regarding previous usage of colistimethate sodium/colistin.

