- number of subjects experiencing bronchospasm clinically or spirometrically determined following IMP administration at the start and end of treatment;
- CCI [redacted] as determined by *in-vitro* CCI [redacted] from Screening/Randomisation (Visit 1/Visit 2) to Visits 3, 5 and end of treatment (Visit 7) as well as on CCI [redacted] from Exacerbation Visits and clinic visits due to pneumonia;
- emergence of other CCI [redacted] and any developing resistance in CCI [redacted] from Screening (Visit 1) to End of Treatment (Visit 7);
- haematology, clinical chemistry and renal function tests;
- physical examination and vital signs data;
- 12-lead electrocardiogram.

Statistical Analysis:

Primary analyses will be performed on the modified intention-to-treat (mITT) population with exclusions from the ITT defined and justified in the Statistical Analysis Plan (SAP). A supportive analysis will be conducted using a per-protocol (PP) population excluding subjects with major protocol deviations.

Annual pulmonary exacerbation rates will be compared between treatment groups using a Poisson regression model allowing for over-dispersion and also considering pooled site, use of stable concomitant therapy with oral macrolides and pulmonary exacerbation frequency in the 12 months preceding Visit 2 as covariates.

The primary analyses detailed above will be a comparison of colistimethate sodium against placebo at the end of the 12-month, double-blind phase. Full details will be provided in the SAP.

The secondary variable of the CCI [redacted] will be analysed using a log-rank test comparing two survival curves. The number of CCI [redacted] will be analysed using an appropriate non-parametric test. The number of CCI [redacted] will also be analysed using a binomial regression model. The absolute changes in CCI [redacted] and the number of days of CCI [redacted] will be presented separately.

CCI scores (CCI total score and CCI [redacted]) will be analysed using linear mixed models.

An analysis of covariance model on log₁₀ transformed values fitting baselines will be used to compare CCI [redacted] between treatment groups.

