19.2. STUDY VARIABLES

Primary Efficacy Variable

The primary variable for this trial is the mean annual NCFB pulmonary exacerbation rate.

Secondary Efficacy Variables

- CCI [REDACTED]
- [REDACTED]
- [REDACTED]
- [REDACTED]
- [REDACTED]
- [REDACTED]
- [REDACTED]

Safety Variables

- the incidence of TEAEs;
- absolute changes in percent-predicted FEV₁ from baseline (Visit 2) to each post-baseline visit;
- the number of subjects experiencing bronchospasm clinically or spirometrically determined following IMP administration at the start and end of treatment;
- CCI [REDACTED] from Screening/Randomisation (Visit 1/Visit 2) to Visits 3, 5 and end of treatment (Visit 7) as well as on CCI [REDACTED] from Exacerbation Visits and clinic visits due to pneumonia;
- emergence of other bacterial colonies and any developing resistance in CCI [REDACTED] from Screening (Visit 1) to End of Treatment (Visit 7);
- haematology, clinical chemistry and renal function tests;
- physical examination and vital signs data;
- 12-lead electrocardiogram.

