19.4.3. SAFETY DATA

All safety endpoints will be summarised and analysed using the Safety Population.

Incidence of Treatment Emergent Adverse Events

The number and the percentage of subjects reporting TEAEs, treatment emergent SAEs, severe TEAEs, TEAEs leading to discontinuation and TEAEs leading to death will be presented by treatment group, along with the number of events occurring.

TEAEs will also be summarised by System Organ Class and Preferred Term according to MedDRA; they will additionally be summarised by severity and relationship to treatment. A separate summary table will be provided for SAEs.

Only TEAEs, i.e. events with an onset date on or after the date of IMP start, will be included in the summary tables. Individual data listings will include all AEs recorded; a separate listing will be provided for treatment-emergent SAEs.

Number of Subjects experiencing Bronchospasm Clinically or Spirometrically Determined following IMP Administration

The number of subjects experiencing bronchospasm spirometrically determined (a >15% decrease in FEV₁ – not due to poor technique - from pre-bronchodilator baseline in the 30 minutes post-IMP), or clinically determined, will be summarised by treatment. Percentages of subjects in each treatment group and the relative risk for colistimethate sodium group/placebo group will be provided with 95% CI. Treatment differences will be assessed using a Fisher Exact test.

The number and the percentage of subjects experiencing a bronchospasm following IMP administration as clinically determined will also be reported.

In addition, the results for FEV₁ and FVC at each visit will be summarised by treatment. Descriptive statistics for absolute and percentage changes from baseline, i.e. Visit 2 (pre-dose measurement) will be reported.

CCI

The number and percentage of subjects whose CCI at the end of treatment (at 12 months [Visit 7]) will be presented by treatment, overall and by status of previous usage of colistimethate sodium/colistin.

Vital Signs

Descriptive statistics for vital signs at Visit 1 and Visit 7 will be presented overall and by treatment.

Physical examination data.

Descriptive statistics for physical examination data at Visit 1 and Visit 7 will be presented overall and by treatment.

Haematology, clinical chemistry and renal function tests

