3.3.1 Trial Flow Chart

VISITS	Visit 1 Screening	Visit 2 Randomisation	Phone call	Visit 3	Visit 4-6	Visit 7 EoT	Follow-Up 'Phone Call	Exacer- bation Visit ^a
ACTIVITIES	Within 30 Days of Visit 2	Day 0	Day 7	Day 28 ± 1 week	Every 3 months ± 1 week	12 months ± 1 week	2 weeks ± 3 days after EoT	-----
Informed consent	X							
Medical history/demography	X							
Pregnancy test	X	X		X	X	X		
Vital signs	X					X		X
Physical examination	X					X		X
Previous/concomitant medications	X	X		X	X	X	X	X
12-lead ECG	X					X		
Obtain blood samples: Haematology and clinical chemistry/Renal Function/PK*	X	X ^c		X ^{a, c}	X ^b	X		
Collect sputum sample	X	X		X	X ^d	X		X
Verify eligibility for randomisation	X	X						
Spirometry: FEV ₁ and FVC	X	X ^e		X	X	X ^e		X
CCI		X		X	X	X		
CCI Training, Dispensing/Collection		X				X		
Review of IMP administration & CCI use (adherence)		X	X	X	X	X		
Study Medication: Dispense/Accountability		X		X	X	X		
Record of hospitalisations and days of work absence			X	X	X	X		X
AE monitoring including exacerbations not otherwise reported	X	X	X	X	X	X	X	X
Weekly follow up phone calls to determine end of Pulmonary Exacerbations								X

^a; renal function test only. ^b; haematology, clinical chemistry and renal function test at Visit 5 (6 Months) only. ^c; PK sampling only (for relevant sites). ^d; Visit 5 only. ^e; FEV₁ and FVC to be measured pre-bronchodilator and 30 minutes post IMP dose.

CONFIDENTIAL

Sponsor:	Zambon S.p.A.	Protocol Number:	Z7224L02
----------	---------------	------------------	----------

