4.13 Changes in Conduct or Planned Analyses from the Protocol

Sections 2.2, 4.4.11, 4.7.5 and 4.7.6.3: The protocol incorrectly referred to the units for the determination of CCI CCI which have been reported as CCI by the central laboratory.

Section 4.7.4: The protocol states that the Negative Binomial Model will consider the log-time on study as offset. However, as specified in Section 4.1.7, NCFB Pulmonary Exacerbations analyses focus on the treatment period so log-time on treatment will be considered.

Sections 4.7.5 and 4.7.6.1: The protocol states that the CCI
[REDACTED]
[REDACTED]. Using date of first IMP as the start time of risk is considered to be biased, so date of randomisation will be used instead.

CONFIDENTIAL

Sponsor:	Zambon S.p.A.	Protocol Number:	Z7224L02
----------	---------------	------------------	----------

Section 4.7.6.1: The protocol states that the CCI [REDACTED] CCI [REDACTED] For time-to-event endpoints, generally the + 1 is not included because this overestimates the time by 1 day for every event, therefore “+ 1” has been deleted.

Section 4.7.6.5: The protocol states that the CCI [REDACTED] total score will be computed and analysed. However, as recommended in the Manual Scoring Instructions [REDACTED], only the CCI [REDACTED] domain scores will be presented and analysed.

There have been no other changes in analyses from those defined in the protocol.

CONFIDENTIAL

Sponsor:	Zambon S.p.A.	Protocol Number:	Z7224L02
----------	---------------	------------------	----------

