5.3.4 Section 14.3: Safety

Table 14.3.1.1	Summary of Treatment Emergent Adverse Events	(Safety Population)
Table 14.3.1.2.1	Treatment Emergent Adverse Events by System Organ Class and Preferred Term	(Safety Population)
Table 14.3.1.2.2	Serious Treatment Emergent Adverse Events by System Organ Class and Preferred Term	(Safety Population)
Table 14.3.1.2.3	Related Treatment Emergent Adverse Events by System Organ Class and Preferred Term	(Safety Population)
Table 14.3.1.2.4	Serious Related Treatment Emergent Adverse Events by System Organ Class and Preferred Term	(Safety Population)
Table 14.3.1.2.5	Treatment Emergent Adverse Events Leading to Permanent IMP Discontinuation by System Organ Class and Preferred Term	(Safety Population)
Table 14.3.1.2.6	Fatal Treatment Emergent Adverse Events by System Organ Class and Preferred Term	(Safety Population)
Table 14.3.1.3.1	Treatment Emergent Adverse Events by System Organ Class, Preferred Term and Maximum Severity	(Safety Population)

CONFIDENTIAL

Sponsor:	Zambon S.p.A.	Protocol Number:	Z7224L02
----------	---------------	------------------	----------

Table 14.3.1.3.2	Related Treatment Emergent Adverse Events by System Organ Class, Preferred Term and Maximum Severity	(Safety Population)
Table 14.3.1.4	Most Frequent Treatment Emergent Adverse Events by Preferred Term ($\geq 5\%$ of Subjects with Events in Any Group)	(Safety Population)
Table 14.3.2.1	Listing of Adverse Events Leading to Death	
Table 14.3.2.2	Listing of Serious Adverse Events	
Table 14.3.2.3	Listing of Adverse Events Leading to Discontinuation of Study Treatment	
Please Note: Section 14.3.3 (Narratives of Deaths, Other Serious and Certain Other Significant Adverse Events) is not to be used for any tables		
Table 14.3.4.1.1	Spirometry: FEV ₁ and FVC Results and Change Versus Baseline	(Safety Population)
Table 14.3.4.1.2	Spirometry: Bronchospasm following IMP Administration at Visit 7 (End of Treatment)	(Safety Population)
Table 14.3.4.2.1	Vital Signs: Results and Change Versus Baseline	(Safety Population)
Table 14.3.4.2.2	Vital Signs: Normal/Abnormal NCS/Abnormal CS Results	(Safety Population)
Table 14.3.4.2.3	Vital Signs: Shift Table	(Safety Population)
Table 14.3.4.3.1	Physical Examination: Results	(Safety Population)
Table 14.3.4.3.2	Physical Examination: Shift Table	(Safety Population)
Table 14.3.4.4.1	12-lead ECG: Results	(Safety Population)
Table 14.3.4.4.2	12-lead ECG: Shift Table	(Safety Population)

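### The SAP compares bronchospasm between arms at Visit 7 only and moves the first-dose result to a listing, an undeclared narrowing of the protocol's safety variable

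*SAP*

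**What the plan says.** Protocol Section 3 (Safety Variables) defines the variable as the "number of subjects experiencing bronchospasm clinically or spirometrically determined following IMP administration at the start and end of treatment", and Section 19.2 repeats it. Section 19.4.3 sets out the analysis: "Percentages of subjects in each treatment group and the relative risk for colistimethate sodium group/placebo group will be provided with 95% CI", plus a Fisher exact test. It names no visit.

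SAP 2.3 lists the same endpoint without the time points. SAP 4.8.2 gives counts, percentages and exact 95% CIs by treatment at Visit 7, and then states: "The number of subjects experiencing bronchospasm at all other visits will be listed". The relative risk and Fisher test follow, with the rule "Subjects with no available result will be excluded from the analysis". The only bronchospasm table in SAP 5.3.4 is Table 14.3.4.1.2, whose title limits it to Visit 7.

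SAP 4.13, which records changes from the protocol, does not mention bronchospasm and closes with: "There have been no other changes in analyses from those defined in the protocol".

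**The concern.** The variable has two time points and the SAP analyses one. The one left out is the first supervised dose, and Protocol 4.1 ties coughing and bronchospasm to the first administration, in roughly 10% of subjects.

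Visit 7 cannot stand in for it. Under Protocol 9.2, 12.2 and 15, an FEV1 fall of more than 15%, or clinical bronchospasm, after the first dose leads to withdrawal. Those subjects do not reach the Visit 7 test, and subjects without a result are dropped from the comparison. The Visit 7 contrast is therefore conditional on having tolerated the first dose, on staying in the trial and on having a supervised in-clinic dose. If the drug provokes bronchospasm at first exposure, the planned between-arm table could look balanced for that very reason.

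**Working it through.** **Text comparison**

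1. *Protocol scope.* Section 19.4.3 names no visit. It is the analysis of the variable defined in 19.2, which covers start and end. That the analysis covers the start follows from reading the two sections together.
2. *SAP scope.* The relative-risk and Fisher sentences in 4.8.2 name no visit either, but they follow the Visit 7 summary and the only planned table is for Visit 7.
3. *What the listing holds.* In the protocol flow chart and both SAP flow charts, only Visits 2 and 7 carry paired spirometry. In SAP 3.3.1 the footnote on those two visits says FEV1 and FVC are "to be measured pre-bronchodilator and 30 minutes post IMP dose". Among scheduled visits, the ones other than Visit 7 therefore reduce to Visit 2.
4. *Declaration.* SAP 4.13 records a change as small as dropping one day from a time-to-event formula, but not this one.

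**Illustration of size**

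The documents give no bronchospasm rate by arm and no power statement for it, so there is no figure to reproduce. The 10% in Protocol 4.1 mixes cough and bronchospasm. All counts and rates below are assumptions. SAP 3.9 reports 287 randomised; 287/2 = 143.5, taken as 143 per arm. The 95% CI is exp[ln RR ± 1.96·SE], with SE = √(1/a − 1/n₁ + 1/b − 1/n₂), where a and b are the colistimethate and placebo counts.

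First dose, 143 per arm:

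- 14 vs 4: RR = 14/4 = 3.50; SE = √(1/14 + 1/4 − 2/143) = 0.554; CI 1.18 to 10.38; Fisher p = 0.026.
- 14 vs 7: RR = 2.00; SE = √(1/14 + 1/7 − 2/143) = 0.448; CI 0.83 to 4.81; p = 0.17.
- 7 vs 7: RR = 1.00; SE = √(2/7 − 2/143) = 0.521; CI 0.36 to 2.78; p = 1.0.

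Visit 7, after 14 vs 4 first-dose withdrawals:

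- Remaining: 143 − 14 = 129 and 143 − 4 = 139.
- If 80% are evaluable: 0.8 × 129 ≈ 103 and 0.8 × 139 ≈ 111.
- With 2 events per arm: RR = (2/103)/(2/111) = 1.08; SE = √(1/2 − 1/103 + 1/2 − 1/111) = 0.991; CI 0.16 to 7.5; p = 1.0.
- With 60% evaluable (77 vs 83) or 90% (116 vs 125), the RR is still 1.08 and the CI almost unchanged.

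Power of a restored first-dose Fisher test is the sum of the two binomial probabilities over all count pairs with two-sided p < 0.05:

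| Colistimethate vs placebo | Power |
|---|---|
| 10% vs 5% | 28% |
| 5% vs 1% | 37% |
| 10% vs 3% | 60% |
| 10% vs 2% | 78% |
| 10% vs 1% | 92% |

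**The case against.** The strongest reply is that little is lost. First-dose reactors are withdrawn for an adverse event, so they should appear by arm in the withdrawal reasons (SAP 4.3) and in the treatment-emergent, related and discontinuation adverse event tables (SAP 4.8.1 and 4.8.1.1). SAP 4.8.2 also summarises the pre- to post-dose FEV1 change by arm at each applicable visit, and under SAP 4.1.3 that summary includes the number with data. Listings are sorted by treatment group (SAP 5.2), and the adverse event listing shows day of onset. All of this stands: a count can be rebuilt by hand. But the adverse event tables do not isolate the first dose or apply the 15% criterion, a mean FEV1 change does not show how many crossed it, and the number with paired FEV1 is not the denominator for a criterion that is clinical or spirometric.

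Visit 7 also answers a real question, since Protocol 4.1 notes that hyperreactivity may develop with continued use. The plan takes trouble to obtain that dose: subjects with a remote Visit 7 are asked to return, and split Visit 7s were used to test for bronchospasm (SAP 4.1.9). That supports keeping Visit 7, not dropping Visit 2.

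SAP 4.1.10 assigns early-termination visits to Visit 7, although 4.1.11 points to listing most such assessments only. Either way, events recorded at Visit 2 do not enter the Visit 7 comparison.

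Finally, Protocol 19.4.3 could be read as one pooled start-or-end count. On that reading too, first-dose events belong in the table. Declaring the change in 4.13 would remove the inconsistency but would not supply the first-dose comparison.

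**Conclusion.** The concern holds. The SAP narrows a protocol-defined safety comparison to the time point from which first-dose reactors are absent, and SAP 4.13 says no such change was made. What is missing is specific: a table with the percentage in each arm meeting the protocol criterion at the first dose, its evaluable denominator, and a relative risk with CI or test.

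The size cannot be stated from the documents. The illustration shows only that a first-dose relative risk of 3.5 could sit beside a Visit 7 relative risk near 1; it rests on invented counts, 143 per arm and an assumed evaluable fraction. A restored Fisher test would have low power except for large differences.

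This is a safety variable outside the efficacy testing hierarchy, no efficacy conclusion depends on it, and part of the information survives elsewhere. It should be fixed, but it does not threaten the trial's main result.

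**What to change.** - In SAP 4.8.2 and Table 14.3.4.1.2, add a block for the supervised first dose at Visit 2 in the Safety Population: n, percentage, exact 95% CI, relative risk with 95% CI and Fisher test, with the number not evaluable in each arm.
- State that the estimates and intervals are the main output, because the test has low power except for large differences.
- Keep the Visit 7 analysis, labelled as conditional on first-dose tolerance, retention and a supervised in-clinic dose.
- Record in SAP 4.13 any departure from the protocol that remains.
- Restore the two time points in the SAP 2.3 endpoint (editorial).

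The cost is SAP wording and one added block in one table. The Visit 2 data are already collected and listed, and no visit, procedure or clinical rule changes.

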9.2. VISIT 2 - RANDOMISATION VISIT (DAY 0)

At Visit 2 (Randomisation), the following procedures will be performed:

- check if subject is still eligible according to the inclusion and exclusion criteria and check of screen failure criteria for Visit 2;
- documentation of concomitant medications (including azithromycin/erythromycin/clarithromycin use) or treatments;
- record details of any AEs since the Screening Visit (Visit 1);
- training and completion of CCI [REDACTED] on the electronic clinical outcome assessment (eCOA) device, or on paper, before other study procedures (Note: paper questionnaires can be used in exceptional circumstances such as when the eCOA malfunctions or because of other technical issues);
- dip-stick pregnancy test for women of child-bearing potential;
- collection of CCI [REDACTED];
- randomisation by Interactive Web Response System (IWRS) and treatment kits assignment;
- dispensing of, and subject training on, CCI [REDACTED] device including the use of the [REDACTED] disc;
- subject training on IMP preparation, inhaled bronchodilator use and subject's card dispensing;
- first IMP administration under clinical supervision (at least 10 minutes after inhalation of 200/180 mcg of short-acting bronchodilator; if the patient prefers not to use a bronchodilator, and the Investigator confirms that the subject can tolerate IMP without it, this should be documented and the lack of bronchial hyper-reactivity after IMP administration documented);
- spirometry, including assessment of FEV₁ and FVC pre-bronchodilator and 30 ± 10 minutes post-IMP dose (**Note:** in case of a >15% decrease in FEV₁ – not due to poor technique - from pre-bronchodilator baseline after first IMP intake, or clinically determined bronchospasm, the subject will be immediately withdrawn from the trial);
- blood samples for pharmacokinetic analysis (selected sites only);
- dispensing of sufficient IMP kits and inhaled bronchodilator for the treatment period until Visit 3;
- instruction of subjects on actions to be taken in case of CCI [REDACTED].

The Investigator will arrange an appointment for Visit 3 (28 days ± 1 week).

In addition, the Investigator will call the subject after 1 week to ensure that there are no problems with the mixing of IMP, the use of the nebuliser device and will also ask about any AEs, including any CCI [REDACTED] due to CCI [REDACTED], and any medical device malfunctions and/or incidents which should be addressed as appropriate.

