4.14 Algorithms/SAS Codes

The SAS codes for descriptive statistics and frequency counts detailed below are examples only and other procedures may be used, if appropriate.

- **Tables that need descriptive statistics – continuous variables:**

```
PROC UNIVARIATE DATA=dset NOPRINT;
  VAR var1 var2 var3 ...varn;
  BY byvar; (optional)
  OUTPUT OUT= outset
  N=n MEAN=mean MIN=min MAX=max MEDIAN=median STD=std *Q1=q1
  Q3=q3; *Include Q1 and Q3 for CCI data only;
RUN;
```

- **Tables that need frequency counts:**

```
PROC FREQ DATA=dset NOPRINT;
  BY byvar; (optional)
  TABLES var1*var2 /out= outset;
RUN;
```

- **Tables that need T-Test;**

```
PROC TTEST DATA=dset;
  CLASS var1;
  VAR var1N;
RUN;
```

- **Tables that need exact 95% CIs for risk difference between groups for proportions and Fisher's Exact:**

```
PROC FREQ DATA=dset;
  BY byvar; (optional)
  TABLES var*treatment / MEASURES RISKDIFF EXACT ALPHA=0.05;
  EXACT MEASURES;
  OUTPUT OUT= outset EXACT MEASURES RISKDIFF;
  WHERE wherever; (optional)
RUN;
```

- **Tables that need 95% CIs within group for binomial proportions:**

```
PROC FREQ DATA=dset;
  BY byvar; (optional)
  TABLES var1;
  EXACT BINOMIAL;
  OUTPUT OUT= outset BINOMIAL;
RUN;
```

- **Tables that require analysis of (co)variance and 95% CIs between arms for continuous variables:**

```
PROC GLM DATA= dset OUTSTAT=outset;
  CLASS treatment psite med;
```

CONFIDENTIAL

Sponsor:	Zambon S.p.A.	Protocol Number:	Z7224L02
----------	---------------	------------------	----------

MODEL change = treatment psite med baseline/ SOLUTION;
LSMEANS treatment / STDERR PDIFF CL OBSMARGINS;
BY byvar; (optional)
WHERE wherever; (optional)

RUN;

Notes:

- Psite represents the country, as detailed in Section 4.9.1;
- Med represents use of stable concomitant therapy with oral macrolides (e.g. azithromycin or erythromycin or clarithromycin) (Yes/No);
- Change represents the change from baseline of the variable;
- Baseline represents the baseline value of the variable;
- Treatment order: 1= Colistimethate Sodium, 2= Placebo.

• **Tables that require Kaplan-Meier estimates and log-rank test:**

PROC LIFETEST DATA=dset OUTSURV=LIFE METHOD=KM timelist=(0 28 90 180 270 EoT) reduceout;

*TIME time*event (1);*
ID subject;
STRATA treatment;
WHERE wherever; (optional)

RUN;

Notes:

- Time represents the time to event or time to censoring;
- Event represents the censoring indicator (1 = censored);

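### SAP 4.8.2 plans only an asymptotic relative-risk CI to compare bronchospasm between arms at Visit 7, and that interval does not exist if either arm has no events

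*SAP*

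**What the plan says.** SAP 4.8.2 plans three outputs for bronchospasm:

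- Within each arm: "The number and percentages (along with exact 95% CIs) of subjects experiencing bronchospasm at Visit 7 (End of Treatment) following IMP administration". Bronchospasm at other visits is only listed.
- Between arms, as an estimate: "The relative risk for colistimethate sodium/placebo will be provided with 95% asymptotic CIs".
- Between arms, as a test: "Treatment differences will be assessed using a Fisher Exact test".

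The section leaves out subjects without a result. It does not say what to report if an arm has no events.

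SAP 4.14 has a code block headed for "exact 95% CIs for risk difference between groups for proportions", paired with Fisher's exact test. Its main line is `TABLES var*treatment / MEASURES RISKDIFF EXACT ALPHA=0.05`. Section 4.8.2 does not mention a risk difference, and 4.14 describes its frequency-count code as illustrative.

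Protocol 19.4.3 is less specific than the SAP: "the relative risk for colistimethate sodium group/placebo group will be provided with 95% CI". It does not fix the method.

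Protocol 9.2 bears on the expected count. After a fall in FEV1 of more than 15% or clinical bronchospasm at the first dose, "the subject will be immediately withdrawn from the trial".

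**The concern.** The asymptotic interval for a relative risk is built on the log scale and needs at least one event in each arm. Visit 7 tests people who got through the first dose without bronchospasm, in a trial that stopped at 287 of 420 randomised, so a count of zero in one arm is a realistic result. The table would then have no interval for the treatment contrast.

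Bronchospasm is a named safety variable, and Protocol 4.1 lists it as a common side-effect of nebulisation. For such an endpoint the useful question is how large an excess the data allow. A p-value does not answer that.

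**Working it through.** **Plan's own figure.** None exists for this comparison. The documents give neither a Visit 7 bronchospasm rate nor a Visit 7 denominator.

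**Inputs.**
- Randomised: 287, allocated 1:1 (SAP 3.9 and 3.1), so about 143 per arm.
- Planned drop-out: about 20% (SAP 3.9). 287 × 0.8 / 2 = 114.8, so about 115 per arm is assumed at Visit 7. The range shown is 100 to 143.
- Risk at Visit 7: assumed, 0.5% to 3%. The only incidence in the documents is about 10% for cough and bronchospasm together at the first administration (Protocol 4.1).

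**Step 1: why the interval fails.** With a events of n₁ on active and b of n₂ on placebo, the 95% limits are

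exp{ ln(RR) ± 1.96 × √(1/a − 1/n₁ + 1/b − 1/n₂) }.

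If a = 0 or b = 0, both ln(RR) and the standard error are undefined.

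**Step 2: how often.** P(no events in an arm) = (1 − p)ⁿ. With equal risk, P(at least one zero arm) = 1 − [1 − (1 − p)ⁿ]². For n = 115 and p = 1%: 0.99¹¹⁵ = 0.315, and 1 − 0.685² = 0.53.

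| Risk in both arms | n = 100 | n = 115 | n = 143 |
|---|---|---|---|
| 0.5% | 84% | 81% | 74% |
| 1% | 60% | 53% | 42% |
| 2% | 25% | 19% | 11% |
| 3% | 9% | 6% | 3% |

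For 3% on active against 1% on placebo with n = 115: 1 − (1 − 0.97¹¹⁵)(1 − 0.99¹¹⁵) = 1 − 0.970 × 0.685 = 34%.

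**Step 3: how often it coincides with a significant excess.** With no placebo events at n = 115, Fisher's test needs 6 active events (p = 0.029; 5 events give p = 0.060). P(no placebo events and at least 6 active events) is:
- 3% against 1%: 0.315 × 0.133 = 4%
- 5% against 1%: 16%
- 5% against 0.5%: 29%

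**Step 4: what the table would show for 6/115 against 0/115.**

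| Quantity | Result | Planned in 4.8.2? |
|---|---|---|
| Active, exact 95% CI | 5.2% (1.9% to 11.0%) | Yes |
| Placebo, exact 95% CI | 0% (0% to 3.2%) | Yes |
| Fisher p | 0.029 | Yes |
| Relative risk, asymptotic 95% CI | Not computable | Yes |
| Relative risk, score 95% CI | Lower limit 1.59, no upper limit | No |
| Risk difference, score 95% CI | 5.2 points (1.9 to 10.9) | No |

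**Step 5: does the 4.14 template fill the gap?** Its heading names the right kind of quantity, but the code has two faults.
- `EXACT` is requested for MEASURES and not for RISKDIFF, so the risk-difference interval would be asymptotic despite the heading.
- `var*treatment` puts the outcome in the rows. RISKDIFF contrasts rows, so it would compare the share of subjects on one treatment between those with and without bronchospasm. For 6/143 against 0/143 this gives 6/6 − 137/280 = 0.51. The between-arm difference is 6/143 − 0/143 = 0.042.

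**The case against.** The case against is substantial on four points.

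1. **The table would not be empty.** Exact within-arm CIs are planned in the same section and hold at zero events. For 5/100 against 0/100 they are 1.6% to 11.3% and 0% to 3.6%. A reader might infer that a real excess could appear with no interval, or with only a p-value. The documents do not support that. It remains true that two one-arm intervals do not estimate the difference between arms.

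2. **SAP 4.14 has a risk-difference template.** No other analysis in the SAP names Fisher's exact test, so the block most plausibly belongs to this table. It would therefore be wrong to say that the relative-risk CI is the only between-arm interval anywhere in the SAP. But 4.8.2 never asks for a risk difference, and the code would not produce the one in its heading.

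3. **The Visit 7 rate is unknown.** A reader might take a zero arm to be the likely outcome. Of the equal risks tabulated, that holds only at about 1% or less. Withdrawal of first-dose reactors lowers the rate by an unstated amount, and Protocol 4.1 says hyperreactivity may develop with continued use. The denominator should not be set too low either: the Protocol summary asks subjects with a remote Visit 7 to return to clinic, and SAP 4.1.9 describes such visits for bronchospasm testing. Also, the equal-risk probabilities in Step 2 describe trials with no true excess and include zeros on active.

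4. **Score intervals can disagree with Fisher.** For 5/100 against 0/100, Fisher gives p = 0.059, while the score limits for the difference (1.2 to 11.2 points) and the lower score limit for the relative risk (1.32) exclude the null. The choice of interval also matters: Agresti-Caffo on the same data includes zero (−0.05 to 9.9 points). This is a real but small cost, which a footnote can cover.

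**Conclusion.** The point holds in limited form. The one between-arm estimate specified in SAP 4.8.2 has an interval that cannot be computed with zero events in an arm, no fallback is stated, and the 4.14 template does not supply one.

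The chance of this is 81%, 53%, 19% and 6% at common risks of 0.5%, 1%, 2% and 3%, and 34% for 3% against 1%. These figures rest on an assumed 115 subjects per arm and on assumed rates, since the documents give neither. A zero arm is plausible but not established as likely.

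What would be lost is the between-arm interval alone. The percentages, their exact CIs and the Fisher test remain. This is a minor improvement to a safety table, with no effect on the primary analysis.

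**What to change.** - **SAP 4.8.2:** add the risk difference (colistimethate sodium minus placebo) with an exact unconditional or score 95% CI, naming which one. Replace the asymptotic CI for the relative risk with a score CI, and state that only the lower limit is reported when the placebo arm has no events.
- **SAP 4.14:** change the table request to `treatment*var`, with RISKDIFF and RELRISK options that match the methods named in 4.8.2, and check that the event column is the one analysed.
- **Table footnote:** say that the interval and the Fisher p-value can disagree near 0.05 and that Fisher remains the stated test.

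The cost is a sentence or two in the SAP, some code options, one more table row and the footnote. The protocol needs no amendment, because it asks for a 95% CI without naming a method. The endpoint definition and the test do not change.
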